8.0 EU-1 Page: 8 of 117 Version

Subjects receive two outpatient telephone contacts, one on Day 2 and one on Day 5. The telephone contact on Day 5 is the final study contact and marks the end-of-study (EOS) for each subject, unless they consent to participate in the Part C Patient-Led Under Medical Supervision Cardioversion Study.

The duration of the Part C Patient-Led Under Medical Supervision Cardioversion Study will continue through the Day 5 telephone contact after a recurrent episode of AF is treated, or approximately 8 months after consent, whichever comes first.

Indication Flecainide acetate inhalation solution is indicated for rapid

> cardioversion of recent onset atrial fibrillation (AF) in patients with symptomatic paroxysmal AF when the need for treatment has been established. Flecainide acetate inhalation solution shall only be used in the absence of any contraindication to

flecainide.

Investigational drug(s) FlecIH-101, FlecIH-102, and FlecIH-103 (flecainide acetate

inhalation solution)

Name of active ingredient Flecainide Acetate

Dose(s) Part A:

> Four doses were evaluated in Part A: 30 mg eTLD, 60 mg eTLD, 90 mg eTLD, and 120 mg eTLD. Each dose was administered using the hand-held inhaler device AeroEclipse® II BAN.

Part B and Part C:

FlecIH-103 (75 mg/mL):

120 mg (repeat dose regimen): 2 consecutive inhalations of 60 mg eTLD

Each dose is administered using the hand-held inhaler device AeroEclipse® II BAN.

Route of administration Oral inhalation

Not applicable Reference drug(s)

Part A Eligibility Criteria Refer to a previous version of the Protocol.

INSTANT Study Clinical Study Protocol

Study no. FLE-002

Version 8.0 EU-1 Page: 9 of 117

Part B and Part C Eligibility Criteria

Subjects to be included in the study must meet the following inclusion criteria:

- 1) Subjects with recent-onset symptomatic AF at presentation.
- 2) With a duration at onset of symptoms from 1 hour to 48 hours
- 3) And from one of the following categories:
 - a) First detected episode of paroxysmal AF
 - b) Recurrent episode of paroxysmal AF
 - c) Episode post-cardiac ablation for paroxysmal AF
- 4) Part C Patient-Led Under Medical Supervision
 Cardioversion Study only: Subjects whose AF converted to SR with inhaled flecainide and without difficulties or issues with inhalation (in the opinion of the investigator), serious AE(s), or serious AESI(s) in Part A, Part B, or the Part C Medically-Led Cardioversion Study

NOTE: Subjects who:

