- are prescribed a pill-in-the-pocket regimen (flecainide or propafenone) for paroxysmal AF, or
- are within 3 months of having undergone ablation of paroxysmal AF, or
- have experienced an episode of new AF but are not currently experiencing an episode of recent-onset paroxysmal AF, or
- are known to have paroxysmal AF (or previously diagnosed with paroxysmal AF) and have one or more previous symptomatic episodes but are not currently experiencing an episode of recent-onset paroxysmal AF

may consent to pre-study screening prior to presenting with recent-onset symptomatic AF. These subjects will be eligible to receive study drug only when presenting with symptomatic paroxysmal AF of recent-onset (i.e., \leq 48 hours), consenting to the full study, and after meeting all eligibility criteria.

INSTANT Study Clinical Study Protocol

Study no. FLE-002

Version 8.0 EU-1 Page: 10 of 117

Subjects are NOT eligible to participate in this study if they meet ANY of the following exclusion criteria:

General

- 1) Subject < 18 or > 85 years of age
- 2) Hemodynamic and/or cardiac instability, with systolic blood pressure < 100 mmHg or > 150 mmHg, and/or ventricular heart rate < 80 bpm or > 160 bpm. For subjects to meet eligibility criteria for Part B or the Part C Medically-Led Cardioversion Study C, at least 2 of the 3 measurements of vital signs during screening (45, 30, and/or 15 minutes prior to dosing) must meet the stated criteria. For subjects to meet eligibility criteria for the Part C Patient-Led Under Medical Supervision Cardioversion Study, the measurement of vital signs taken within 10 minutes prior to dosing must meet the stated criteria.
- 3) Current AF episode treated with Class I or Class III antiarrhythmic drugs or electrical cardioversion. Subjects whose current AF episode has been treated with flecainide are eligible if their total cumulative exposure to flecainide (including the study drug to be administered in this study) does not exceed 320 mg within a 24-hour period, per site standard of care.

Relevant structural heart disease

- 4) History of acute decompensated heart failure (HF)
- 5) Evidence of significant HF defined as any of the following:
 - a) Hospitalization in the last 12 months for HF or suspected HF event
 - b) Most recent assessment of left ventricular ejection fraction (LVEF) < 45%

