 - i) For subjects in the US, a standard diagnostic echocardiogram assessed ≤ 180 days prior to screening is required to ascertain eligibility. If none is available, the subject must undergo a standard diagnostic echocardiogram or a diagnostic echocardiogram using a portable ultrasound device (handheld echocardiogram [HHE]) during screening to confirm eligibility.

INSTANT Study Clinical Study Protocol

Study no. FLE-002

Version 8.0 EU-1 Page: 11 of 117

- ii) For subjects in the EU who are participating in the optional HHE Sub-Study, the subject must undergo an HHE during screening to confirm eligibility.
- New York Heart Association (NYHA) Class II-IV symptoms
- d) Medication history suggestive of HF per the Investigator's discretion
- 6) Evidence of current ongoing myocardial ischemia, such as signs (e.g., significant [e.g., > 2 mm] ST segment elevation or depression on ECG, echocardiographic findings suggestive of acute myocardial infarction), symptoms (e.g., angina pectoris, atypical angina pectoris), and/or being medicated with anti-anginal medication. In addition, subjects with signs of prior myocardial infarction (such as pathological Q waves) who are also taking concomitant medications for angina pectoris should be evaluated for presence of ongoing ischemia.
- 7) History of myocardial infarction (MI) within 3 months of screening
- 8) Known uncorrected severe aortic or mitral valve stenosis. For subjects receiving an HHE assessment at screening (refer to exclusion criterion 5), any moderate or severe valvular disease noted during the HHE assessment is considered exclusionary.
- 9) Hypertrophic cardiomyopathy with outflow tract obstruction. For subjects receiving an HHE assessment at screening (refer to exclusion criterion 5), any moderate or severe hypertrophy noted during the HHE assessment is considered exclusionary.

Other cardiac conditions

- 10) Current diagnosis of persistent AF
- 11) One or more episodes of atrial flutter within 6 months prior to screening or atrial flutter at presentation, except subjects who received ablation for atrial flutter at least 3 months prior to screening and had no subsequent recurrence of atrial flutter prior to enrollment
- 12) History of any of the following heart abnormalities:
 - a) Long QT syndrome
 - b) Conduction disease (e.g. second- or third-degree heart block, bundle branch block)

INSTANT Study Clinical Study Protocol

Study no. FLE-002

Version 8.0 EU-1 Page: 12 of 117

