Class Ic AADs (such as flecainide) are also well known to be arrhythmogenic properties. The same or similar ion channel and electrophysiological effects that explain the therapeutic effects of flecainide are considered to be responsible for its proarrhythmic activity. The inhibition by flecainide of peak I_{Na} is exacerbated in depolarized myocytes and at high frequencies of depolarization (i.e., fast heart rates). Consequently, inhibition of peak I_{Na} in diseased myocardium may cause marked rate-dependent slowing of conduction and facilitate the initiation of re-entrant wave fronts around lines of functional conduction block such as infarcted or fibrosed tissue, leading to life-threatening ventricular arrhythmias and sudden cardiac death. It is important to recognize that the proarrhythmic effects of flecainide have been observed primarily in patients with ischemic heart disease, depressed LV function (e.g., HF), electrolyte disturbances, congenital (genetic) and acquired diseases/conditions resulting in conduction abnormalities. The results of the Cardiac Arrhythmia Suppression Trial (CAST)³⁴ demonstrated that flecainide, like other Class Ic AADS, caused serious malignant arrhythmias that led to a 3.6% (95% CI, 1.7 to 8.5) increase in risk of non-fatal cardiac arrest and death from arrhythmia compared to placebo. Due to this proarrhythmic potential, patients with depressed LV function, ventricular scar tissue and ischemic myocardium should not be treated

INSTANT Study Clinical Study Protocol

Study no. FLE-002

Version 8.0 EU-1 Page: 29 of 117

with flecainide. In addition, the negative inotropic effect of flecainide is greater in patients with LV dysfunction. Directly related to the proarrhythmic effects of flecainide caused by marked inhibition of peak I_{Na}, is the excessive widening of the QRS interval and/or slowing of the AV nodal conduction (PR prolongation or AV nodal block). These are important premonitory signs of the impending arrhythmogenic effects of flecainide.

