1.3 Rationale for the study

The aim of inhaled flecainide (in patients that have no contraindications for IV or oral flecainide) is the restoration of SR in symptomatic patients with recent onset AF (of < 48 hours) in a manner that is safe, rapid (in minutes) and convenient. Minimizing the time spent in AF is consistent with the concept that "sinus rhythm begets sinus rhythm" and may decrease the frequency of recurrences, and thereby slow/delay the progression of paroxysmal to persistent and/or permanent AF.

INSTANT Study Clinical Study Protocol

Study no. FLE-002

Version 8.0 EU-1 Page: 35 of 117

Part A - Initial data for inhaled flecainide suggest that cardioversion of subjects with recent onset of paroxysmal AF may be achieved within minutes with the possibility to eliminate the inhospital administration in the long term. Before embarking on further stages of the clinical development plan for inhaled flecainide, it was important to ascertain that flecainide, at the dose and regimens to be tested, is well tolerated and that the study is feasible. Therefore, Part A of the current study was devised as an open-label, dose-escalation investigation to evaluate the feasibility and tolerability of several inhalation regimens of inhaled flecainide. Although no conclusions about the effectiveness of inhaled flecainide can be drawn from the results of Part A, the aims of the study were to provide supportive data on the viability, acceptability and tolerability of the study design and procedures prior to proceeding into Part B to confirm the efficacy of the selected dose using an open-label study design.

Part B is an open-label multi-center design to confirm the safety (including tolerability) and to provide a more precise estimate of efficacy of the optimal inhaled flecainide dose regimen determined from Part A. The planned dose is an eTLD of 120 mg given as two sequential inhalations (repeat regimen, 2×60 mg eTLD = 120 mg eTLD). Subjects will 'dose/inhale to conversion'; dosing in a 'dose/inhale to conversion' regimen continues according to the assigned regimen until the conversion of AF to SR is observed for ≥ 1 minute, or until the assigned dose is completed, whichever comes first. The study drug is administered to subjects with a recent onset of symptomatic AF without relevant structural heart disease.

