1.5 Benefit/Risk assessment

This is the first study investigating inhaled flecainide acetate for acute conversion of recent onset of paroxysmal AF to SR. Based on the data from Part A of the study, the doses of flecainide acetate inhalation solution (30 mg eTLD, 60 mg eTLD [2 x 30 mg eTLD], 90 mg eTLD [2 x 45 mg eTLD], and 120 mg eTLD [2 x 60 mg eTLD]), were safe in 101 subjects. The 120 mg eTLD selected for Part B provides an acceptable benefit/risk in this population:

Study no. FLE-002

Version 8.0 EU-1 Page: 37 of 117

a) The potential cardiovascular risks of oral and IV flecainide are monitored closely in clinical studies of oral inhaled flecainide (AEs of special interest): ventricular tachycardia (VT), hypotension, bradycardia, sinus pause post conversion of AF to SR, and atrial flutter with 1:1 conduction with fast ventricular response (ventricular heart rate ≥ 200 bpm).

- i) Ventricular tachycardia (VT) is rare in subjects without structural heart disease, electrolyte disturbances and coronary artery disease. Ventricular proarrhythmia manifests either as monomorphic or polymorphic VT not only early but also late after the initiation of chronic therapy³⁴. The incidence of VT in patients receiving flecainide for acute cardioversion of atrial fibrillation is less than 3%⁴⁵. These potential risks have been mitigated by excluding subjects who have structural heart disease, myocardial ischemia, and LV systolic dysfunction, populations in which these adverse effects are more commonly encountered.
- ii) Due to a negative inotropic effect, flecainide is contraindicated in subjects with congestive heart failure and reduced LV ejection fraction (LVEF)^{46, 47}. Therefore, these subjects have been excluded from the current study population.
- iii) Clinically significant slowing of electrical conduction have been reported with chronic oral flecainide therapy, including exacerbation/unmasking of conduction system disturbances, such as sinus node dysfunction (1.2%; i.e., sinus pause, sinus arrest or symptomatic bradycardia). Flecainide alone may cause bradycardia, second-degree AV block (0.5%) or third-degree AV block (0.4%). Flecainide slows cardiac electrical conduction because it inhibits peak I_{Na}, which is the basis for the contraindication for its use in patients with conduction system disturbances.

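### Exclusion 7 bars MI only within 3 months, although section 1.1 says patients with ventricular scar should not receive flecainide; an older uncomplicated infarct with LVEF ≥ 45% meets no specific numbered exclusion

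*Protocol*

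**What the plan says.** Protocol section 1.1 describes how sodium-channel block in diseased myocardium can start re-entry "around lines of functional conduction block such as infarcted or fibrosed tissue, leading to life-threatening ventricular arrhythmias and sudden cardiac death". It concludes that "patients with depressed LV function, ventricular scar tissue and ischemic myocardium should not be treated" with flecainide, and puts no time limit on scar.

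Section 1.5, item a) i), says VT is rare without structural heart disease, electrolyte disturbance or coronary artery disease, and continues: "These potential risks have been mitigated by excluding subjects who have structural heart disease, myocardial ischemia, and LV systolic dysfunction".

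The criteria meant to deliver this are exclusions 4 to 9, grouped under the heading "Relevant structural heart disease". Two matter most here. Exclusion 5b is "Most recent assessment of left ventricular ejection fraction (LVEF) < 45" (percent). Exclusion 7 is "History of myocardial infarction (MI) within 3 months of screening", identical in the synopsis and in 4.2 B.

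General wording sits outside the numbered list. Section 1.3 says that "The study drug is administered to subjects with a recent onset of symptomatic AF without relevant structural heart disease". Sections 3 B and 6 B describe candidates in similar terms, and 6 B adds that they have no contraindication to flecainide. The synopsis indication says the drug "shall only be used in the absence of any contraindication to" flecainide.

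**The concern.** The protocol states a class of patient who should not be given the drug and then sets an entry rule that does not exclude that class. An infarct does not stop being infarcted tissue after 3 months, and section 1.1 names such tissue as the substrate for lethal arrhythmia. Sites enroll from the numbered list, so read literally it can admit a patient whom the introduction says not to treat. The mitigation claimed in section 1.5 is then only partly delivered.

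This bears on a stated endpoint: sustained VT, torsades de pointes and ventricular fibrillation are serious adverse events of special interest (SAESIs; 9.1.2.4 B, SAP Annex A), and the incidence of treatment-emergent SAESIs is the secondary safety endpoint (7.5.2 B, SAP 6.2.3).

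**Working it through.** No arithmetic applies. The check takes one hypothetical subject through the criteria: MI more than 3 months before screening, LVEF ≥ 45%, no heart failure, no ongoing ischemia, no anti-anginal drug, QRS below 120 ms, no VT before dosing, otherwise eligible.

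**Structural group (exclusions 4 to 9)**
- 4 and 5 (heart failure, LVEF < 45%): not met. LVEF measures pump function; 5b does not ask about scar.
- 6 (current ischemia): not met. It mentions signs of prior infarction, such as Q waves, but asks only that subjects who have them and also take angina medication be assessed for ongoing ischemia. Prior infarction was therefore foreseen and left eligible.
- 7: not met, because the infarct lies outside the window.
- 8 and 9 (valve stenosis, obstructive hypertrophic cardiomyopathy): not met.

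**Remaining exclusions**
- 12b, 13b and 13d (conduction disease, wide QRS, pre-dose VT or frequent ectopy): not met by this subject, though they would catch some patients with scar.
- 29 lists coronary artery disease among its exclusionary conditions but bars only cardiac surgery within 6 months. No criterion excludes coronary disease as such.
- The others (1 to 3, 10, 11, 14 to 21, 23 to 28, 30) do not concern prior infarction.
- 22 leaves the decision to the investigator; its examples name neither infarction nor scar.

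Of 30 exclusions, 30 − 1 = 29 are specific, and the subject meets 0 of the 29.

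**Stated reason for the window.** Sections 1.1, 1.3, 1.4, 1.5 and 4.2 B give none.

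**Echocardiography.** US subjects need a standard echocardiogram within 180 days, or an echocardiogram at screening. EU subjects must have a handheld echocardiogram only if they join the optional sub-study; otherwise exclusion 5b rests on the most recent LVEF. Imaging is therefore not guaranteed for every subject.

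**The case against.** The strongest reply is that the protocol should be read as a whole. The heading over exclusions 4 to 9 sends a site that looks up relevant structural heart disease back to the 3-month rule, but the contraindication wording in the synopsis and 6 B does not. The protocol's own account of who should not receive flecainide is section 1.1, which names scar. On that reading a site is already told not to dose a patient with known scar, and what remains is a drafting gap. This is largely right and sets the scale of the point. It does not remove it: the contraindication wording is unnumbered and does not name infarction, while a specific time limit invites the inference that an older infarct is acceptable.

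Other safeguards also count: exclusions 12b, 13b and 13d, dosing under cardiac monitoring in hospital, and any echocardiogram performed. They reduce risk; none of them excludes old infarction.

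The missing rationale is weak evidence alone. Other windows, such as 12 months for heart failure hospitalization and 6 months for flutter, have none either, and the Investigator's Brochure and Summary of Changes are separate documents not available here. The point rests on the mismatch with section 1.1. It is also fair that not every old infarct with preserved LVEF is documented ventricular scar; the documents do not equate the two.

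Three stronger inferences are not supported:
- *No VT occurred in 101 subjects, so the window is safe.* Section 1.4 itemizes only related SAEs, in four subjects (two sinus pauses, one bradycardia, one atrial flutter with 1:1 conduction). It shows that none of these was VT. It says nothing about non-serious VT, and it does not say how many subjects had a prior infarct.
- *The handheld echocardiogram rule lets visible scar through.* SAP 9.2.4.2 derives eligibility from four items, none of them scar. But protocol 17.5.1 and 17.5.3 exclude clinically significant structural disease, and 17.5.4.1 records other significant findings. The six handheld studies in SAP 1.3 are also not a count of all subjects with an echocardiogram.
- *Patients with old infarcts were dosed and harmed.* Neither document reports one.

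**Conclusion.** The concern holds as an inconsistency between the protocol's statement of who should not be treated and its numbered criteria. It should be corrected. The gap is narrow: an uncomplicated infarct older than 3 months, LVEF ≥ 45%, no ongoing ischemia and no anti-anginal drug. It is narrowed further by exclusion 22 and the general wording, without being closed.

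Its size cannot be stated. The documents give no frequency of older infarction, no count of such subjects and no event in one. The conclusion rests on two assumptions: that sites apply the numbered list as written, and that an older infarct can leave the infarcted or scarred tissue section 1.1 warns about. A justification of the window outside these documents would reduce the point to a need to state it and align the text.

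**What to change.** In the synopsis and in 4.2 B, change exclusion 7 to *any history of MI, or known ventricular scar*. If the 3-month window is intended, justify it and amend sections 1.1 and 1.5 to say that older infarcts with preserved LVEF are admitted.

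The cost is wording in two places and slightly fewer eligible subjects. Enrollment in the Part C medically-led study stopped on 31 December 2021 (SAP 1.1.1), so the change cannot alter who entered it. It corrects the stated risk mitigation and applies to any reuse of the list. SAP 1.1.1 says this dose and formulation was selected for Phase 3; it does not say the eligibility list will be carried over.

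As an optional convenience, add a prior-MI flag to the AESI and SAESI listings; the flags in SAP 9.2.2.9 do not include one. Medical history is already coded and listed (SAP 9.1) and covered by Table 1, and listings are sorted by subject, so a reader can cross-reference without the flag.

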INSTANT Study Clinical Study Protocol

Study no. FLE-002

Version 8.0 EU-1 Page: 17 of 117

the Sponsor to support rollover participation in the Part C Patient-Led Under Medical Supervision Cardioversion Study (refer to description above).

All subjects enrolled and treated with study drug will be analyzed within the safety population. For the modified intention-to-treat population (mITT), for any subject who was not in AF at the time of dosing and who does not complete inhalation of the full assigned dose will be replaced to keep the sample size needed.

In Part B, the estimated sample size of 25 subjects for the 120 mg dose cohort is based upon the evaluation of the following statistical hypotheses using an exact binomial test,

$$H_0$$
: $\rho = 20\%$ versus H_A : $\rho > 20\%$ ($\alpha = 0.05$).

Given the actual conversion rate for the Part A 120 mg dose cohort (FlecIH-103 inhalation solution) is 48%, a sample size of 25 subjects has at least 92% power to reject the null hypothesis (H_0) in favor of the alternative (H_A) with a one-sided significance level of 0.05. The null hypothesis is rejected when at least 9 subjects' AF converts to SR within 90 minutes after initiation of dosing.

For example, with 25 subjects enrolled in Part B, if 9 of them have their AF converted to SR, the resulting conversion rate is 36% with a 90% exact binomial confidence interval of [20.24%, 54.39%]. If 9 or more subjects' AF converts to SR, the lower bound of the 90% exact binomial confidence interval will be greater than 20.24%. When the lower bound of the 90% confidence interval for conversion rate is greater than 20%, there is sufficient support for the rejection of the null hypothesis in favor of the alternative.

It is expected approximately 20 subjects will participate in the HHE Sub-Study in Europe (Part B and the Part C Medically-Led Cardioversion Study); however, the HHE Sub-Study does not have a minimum or maximum enrollment target.

Statistical analyses

INSTANT Study

Clinical Study Protocol

Study no. FLE-002

Version 8.0 EU-1 Page: 18 of 117

PART A:

The main feasibility, efficacy and safety parameters were presented in a descriptive manner. Data on PK, PD and other assessments were presented in a similar manner.

PART B:

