All (primary and secondary) efficacy endpoints are analyzed with the *modified Intention-to-treat (mITT) population*. The mITT population is defined as all enrolled subjects who were in AF at the time of dosing and completed the full assigned dose of study drug.

The primary endpoint analyses of Part B will be based on Part B subjects alone. If the Part B primary endpoint analysis meets the pre-specified criteria for significance and is not substantially different from Part A 120 mg FlecIH-103, the two dose cohorts (120mg FlecIH-103 cohorts from Part A and Part B) will be combined for the overall analysis of Part B to provide a more precise estimate of efficacy, safety, and PK/PD.

The primary efficacy analyses will compute the proportion of subjects whose AF converted to SR within 90 minutes after initiation of dosing. For Part B, the primary analysis will be based upon one-sided testing (i.e., $\rho > 20\%$) via an exact binomial test. One-sided testing is being undertaken based on the results from Part A with the same dose showing a conversion rate of 48%. A one-sided binomial exact test will be used to determine whether the null hypothesis of equality may be rejected in favor of a conversion rate of greater than a historical placebo rate of approximately 20%, a value higher than reported for placebo in the literature (16%)³ and in the more recent randomized, placebo-controlled trials with vernakalant (approximately 5%)⁴.

PART C:

No formal hypothesis testing is planned for Part C. Summary statistics will be generated, including estimates of the endpoints with their associated 90% confidence intervals.

All statistical analyses performed in the evaluation of the INSTANT Study data are described in the statistical analysis plan (SAP).

Study no. FLE-002

Version 8.0 EU-1 Page: 19 of 117

V. Table of contents

I.	CLINICAL STUDY TITLE PAGE	1
II.	PROTOCOL APPROVAL PAGE	2
III.	SIGNATURE PAGE PRINCIPAL INVESTIGATOR	3
IV.	PROTOCOL SYNOPSIS	4
٧.	TABLE OF CONTENTS	19
VI.	LIST OF TABLES	24
VII.	LIST OF IN-TEXT FIGURES	24
VIII.	LIST OF ABBREVIATIONS	25
IX.	INTRODUCTION	26
1	INTRODUCTION	26
1.1	FLECAINIDE ACETATE	27
1.2	FLECAINIDE ACETATE INHALATION SOLUTION (FLECIH)	29

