10.1.3 B - Modified ITT population (mITT)

The modified ITT population includes all enrolled subjects who received the full assigned dose of study drug and were in AF at the time of start of the inhalation of the study drug. Subjects whose AF converted to SR prior to completion of the assigned full dose of study drug will also be included in the mITT population.

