10.3 B - Sample size determination

In Part B, the estimated sample size of 25 mITT subjects for the 120 mg dose cohort is based upon the evaluation of the following statistical hypotheses using an exact binomial test, H_0 : $\rho = 20\%$ versus H_A : $\rho > 20\%$ ($\alpha = 0.05$).

Given the actual conversion rate for the Part A 120 mg dose cohort is 44%, a sample size of 25 subjects has 84% power to reject the null hypothesis (H_0) in favor of the alternative (H_A) with a one-sided significance level of 0.05. The null hypothesis is rejected when at least 9 subjects' AF converts to SR within 60 minutes after initiation of dosing.

If 9 subjects' AF converts to SR, the resulting conversion rate is 36% with a 90% exact binomial confidence interval of [20.24%, 54.39%]. If 9 or more subjects' AF converts to SR, the lower bound of the 90% exact binomial confidence interval will be greater than 20.24%. When the lower bound of the 90% confidence interval for conversion rate is greater than 20%, there is sufficient support for the rejection of the null hypothesis in favor of the alternative.

It is expected approximately 20 subjects will participate in the Handheld Echo Sub-Study in Part B and the Part C Medically-Led Cardioversion Study; however, the Sub-Study does not have a minimum or maximum enrollment target.

Study no. FLE-002

Version 8.0 EU-1 Page: 78 of 117

XII. Study protocol (Part C - EU only): Medically-Led Cardioversion and Patient-Led Under Medical Supervision Cardioversion Studies

2 C - Study objectives

All Part C objectives are exploratory:

- To explore the feasibility of patient-led self-administration of flecainide acetate inhalation solution in a hospital setting under medical supervision
- To explore the PK/PD of flecainide acetate inhalation solution in subjects with recent onset of paroxysmal AF for patient-led administration relative to medically-led administration, including resumption of SR
- To explore the feasibility of implementing a portable cardiac ultrasound (HHE) at screening in an emergent setting

3 C - Study design

Part C is conducted in Europe only. Part C comprises two distinct studies, a Medically-Led Cardioversion Study (procedures are identical to those in Part B) and a Patient-Led Under Medical Supervision Cardioversion Study (procedures include the subject self-preparing and self-administering the study drug under medical supervision in the clinic).

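### The Part B replacement rule joins the two grounds for leaving the mITT with 'and', so read literally it does not assure the 25 mITT subjects behind the stated power

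*Protocol*

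**What the plan says.** **Replacement.** The protocol synopsis, under Planned sample size, replaces "any subject who was not in AF at the time of dosing and who does not complete inhalation of the full assigned dose". The same sentence gives its purpose as preserving the required sample size. The only other replacement provision, in Section 5.5 B and repeated in SAP Section 1.7, concerns subjects who were enrolled but never dosed. The synopsis adds that untreated subjects do not count towards the planned number.

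**mITT membership.** The synopsis (Statistical analyses) and Section 10.1.3 B require both AF at the start of inhalation and the full assigned dose. Section 10.1.3 B makes one exception: "Subjects whose AF converted to SR prior to completion of the assigned full dose of study drug will also be included in the mITT population". SAP Section 8.5 agrees, treating an early stop because of conversion as completing the assigned dose.

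**Sample size.** Section 10.3 B refers to "the estimated sample size of 25 mITT subjects for the 120 mg dose cohort". The synopsis says that "a sample size of 25 subjects has at least 92% power" at an assumed rate of 48%. Section 10.3 B says: "Given the actual conversion rate for the Part A 120 mg dose cohort is 44%, a sample size of 25 subjects has 84% power". Both reject the null hypothesis at 9 or more conversions.

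**The concern.** A subject belongs to the mITT if in AF *and* fully dosed (or converted early). The complement is a subject who was not in AF *or* was not fully dosed. The replacement rule instead names subjects who fail both conditions, which is a much smaller set than the one it has to refill.

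That smaller set should be close to empty. Section 6.2.1 B does not allow inhalation to start in a subject who is out of AF, so a double failure needs a breach of that step together with an incomplete dose. The exclusion to be expected is a subject in AF who does not finish inhaling. That is the reason Section 1.4 gives for both FlecIH-103 exclusions in Part A, and the literal rule would not have replaced either of them.

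What is at stake is power. The stated figures and the threshold of 9 belong to an analysis of 25 mITT subjects, and the sentence meant to protect that number does not do so as worded.

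**Working it through.** **Inputs**
- Test: exact binomial, "with a one-sided significance level of 0.05" (synopsis).
- Null rate: "historical placebo rate of approximately 20"% (synopsis, Statistical analyses).
- Assumed rate, synopsis: "conversion rate for the Part A 120 mg dose cohort (FlecIH-103 inhalation solution) is 48"%, from 13/27 in Section 1.4. Assumed rate, Section 10.3 B: 44%. Both are carried through.
- Exclusions in Part A (Section 1.4): 2 of 29 treated with FlecIH-103, both for an incomplete dose; 2 of 19 with FlecIH-102, also for an incomplete dose.

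**Step 1: reproduce the plan's figures.** With X ~ Binomial(25, p) and rejection at X ≥ 9:
- Type I error: P(X ≥ 9 | p = 0.20) = 0.0468.
- Power: P(X ≥ 9 | p = 0.48) = 0.9205, and P(X ≥ 9 | p = 0.44) = 0.843.
- Clopper-Pearson 90% interval for 9/25: 20.24% to 54.39%.

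These match the stated 92%, 84% and interval.

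**Step 2: power if exclusions are not replaced.** For each mITT size n, take the smallest r with P(X ≥ r | n, 0.20) ≤ 0.05, then compute P(X ≥ r | n, p).

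| mITT n | r | Type I error | Power at 48% | Power at 44% |
|---|---|---|---|---|
| 25 | 9 | 0.047 | 92.0% | 84.3% |
| 24 | 9 | 0.036 | 89.2% | 80.1% |
| 23 | 9 | 0.027 | 85.6% | 75.0% |
| 22 | 9 | 0.020 | 81.0% | 69.1% |

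The threshold stays at 9 throughout this range, so each lost subject lowers power without lowering the bar.

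**Step 3: how many losses to expect.** Assume 25 treated, no replacement, and an independent exclusion probability d for each subject. Then the expected mITT size is 25(1 − d), the chance that all 25 qualify is (1 − d)^25, and average power is the Step 2 power (r reset at each n) weighted by the Binomial(25, 1 − d) distribution of n.

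| d | Expected n | Chance all 25 qualify | Average power at 48% | at 44% |
|---|---|---|---|---|
| 2/29 = 6.9% (FlecIH-103) | 23.3 | 17% | 87% | 77% |
| 2/19 = 10.5% (FlecIH-102) | 22.4 | 6% | 85% | 75% |

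The rate is poorly known: the exact 95% interval for 2/29 runs from about 0.8% to 22.8%.

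**Step 4: size of the remedy.** At d = 2/29, reaching 25 mITT subjects takes about 25 / (27/29) = 26.9, so 27 treated subjects.

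**Step 5: overfilling.** At n = 26 the threshold moves to 10 (type I error 0.023) and power drops to 87.9% at 48% (77.7% at 44%). Going past 25 therefore also costs power, which matters for how the corrected rule is worded.

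**The case against.** The strongest reply is that the intent is plain. The sentence states its own purpose, Section 10.3 B sets the target in mITT subjects, and no passage caps recruitment at 25 treated; the planned number is only approximate. The sentence is also grammatically loose enough to be read as listing two kinds of subject. On that reading a sponsor would simply recruit to 25 mITT subjects. This stands as far as it goes: a reader might infer from the 'and' that 25 mITT subjects will not be reached, and the documents do not support that. A shortfall needs the literal reading, roughly 25 treated, and at least one subject failing a single condition. Evident intent is nevertheless a reason to correct the wording, because no other passage supplies a rule for treated subjects.

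A reader might also infer that the present rule wrongly replaces early converters. It does not. They were in AF at dosing, so the literal 'and' never reaches them. They matter only when the rule is rewritten with 'or'.

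The effect is moderate. One or two losses leave 86% to 89% power at 48%, and the exact test remains valid at a smaller n.

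Timing is a further limit. The supplied SAP is the final-analysis plan, and its Section 9.3 describes the Part B pooling test as already done. The Part B versions, V4.0 and V4.1, are not available. The version history says V4.1 revised the mITT population, so whether either clarified replacement is unknown.

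**Conclusion.** The point holds as a wording defect that leaves the sample-size target unprotected. The replacement rule does not match the set of subjects excluded from the mITT and, read literally, omits the usual exclusion. The possible cost is about 3 percentage points of power at 48% for one unreplaced exclusion and about 6 for two (92.0% to 89.2% to 85.6%). At 44% it is about 4 and 9 points (84.3% to 80.1% to 75.0%). The average figures of about 87% and 77% assume 25 treated, no replacement, and an exclusion rate taken from two subjects in Part A. Neither the validity of the test nor its type I error is in question.

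**What to change.** Reword the synopsis sentence along these lines: *any treated subject who was not in AF at the start of dosing, or who did not complete the full assigned dose for a reason other than conversion to SR, will be replaced until 25 mITT subjects are reached.* The exception for converters is needed. Changing 'and' to 'or' on its own would also replace subjects whom Section 10.1.3 B keeps in the mITT, and would push n past 25 (Step 5). The same rule should be stated in Section 10.3 B, next to the target.

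The cost is one sentence and, at the Part A rate, about two further treated subjects, consistent with the rule's stated purpose.

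If Part B enrolment has closed, the study report should give the numbers treated, excluded from the mITT (by reason) and replaced, say which reading of the rule was applied, and give the rejection threshold and power at the mITT size achieved.
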